8.0 STATISTICAL METHODS

8.1 Sample Size

Aim 1 (Survey): A sample size of 1090 eligible subjects is required to address Specific Aim 1. We have chosen this sample size based on our preliminary study (Section 2.9), from which we can assume that 90% (n=981) of those approached will participate in the survey. A sample of 981 survey participants for Specific Aim 1 will provide 80% power to reject the null hypothesis that the prevalence (p) of HPV vaccine initiation is ≤ 0.4 if the true p is at least 0.44 (one-sided test, Type I error=0.05). It will also provide a 2-sided 95% confidence interval (CI) of sample $p \pm .061$ if true $p=0.4$.

[Protocol v3, 8/17/15: Accrual goal for Aim 1 met, enrollment to survey closed]

Aim 2 (Vaccine Evaluation):

qHPV Vaccine Cohort (patients enrolled on or before 3-1-16): Based on national vaccine initiation rates and our preliminary data (Section 2.9),⁴⁰ we conservatively assume that 60% (n=589) of the 981 survey participants will have not initiated the HPV vaccine. Based on our data (Section 2.9) and prior trials,^{30,31,135} we conservatively assume that of the non-vaccinated survey participants, 60% (n=353) will agree to receive the vaccine, 96% (n=339) will be seronegative at baseline (Intent to Treat [IT] sample), and 92% (n=312) will complete all 3 doses, yielding 312 (Per-Protocol [PP]) subjects who will have received all 3 doses of qHPV vaccine for examining Aim 2.1. This sample size was calculated using the mean GMT and SD reported by Merck & Co.²⁸ for healthy males and females aged 9-15 years and 16-26 years as the historical healthy population. The following assumptions were made: i) cancer survivors were similarly distributed in regard to immunogenicity with the same SD as in this healthy population; ii) margin of equivalence (E) was $\frac{1}{2}$ of the mean GMT of the healthy population (Table 7). Using the method of Korn and Freidlin¹³⁶ for sample size calculations using historical controls, a total of 312 subjects (72 younger females, 77 older females, 82 younger males, and 81 younger males) will provide 80% power to demonstrate non-inferiority with respect to anti-HPV-16, and/or -18 GMT in cancer survivors compared to the healthy population assuming a one-sided t-test, Type I error =0.00312 (for an overall Type I error =0.025), and margin of equivalence (E) shown in Table 7 by sex and age for each vaccine type.

Table 7. Sample Size for Aim 2 (Vaccine Evaluation)

		Females								

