Anti-HPV	9-15y (younger)					16-26y (older)				
	Healthy	Cancer	E	SD	N	Healthy	Cancer	E	SD	N
16	4918.5	2459.3	2459.25	5585.26	72	2411.3	1205.65	1205.65	2915.77	77
18	1042.6	521.3	521.30	1161.91	69	475.6	237.80	237.80	500.01	58
		Males								
16	6056.5	3028.3	3028.25	6895.81	72	2401.5	1200.75	1200.75	2747.45	72
18	1357.4	678.7	678.70	1641.08	82	402.6	201.30	201.30	489.9	81

Sample size required = 312

The coordinating center will track enrollment to each stratum (Younger Females, Older Females, Younger Males, Older Males), and will close enrollment to each stratum once the targeted number of evaluable participants has been reached.

9vHPV Vaccine Cohort (patients enrolled after 3-1-16): Results of interim data analysis on the qHPV vaccine cohort (performed in January 2016 with data from patients who had a Month 7 sample available for analysis on or before 8-28-15; N=133) indicate that the cohort enrolled on or before 3-1-16 (N=254) who have received/are receiving the qHPV vaccine will be more than sufficient to address non-inferiority (i.e., lower limit of the multiplicity-adjusted 95% confidence intervals for the ratio of the mean geometric mean titer for anti-HPV-16 and -18 in the cancer vs. healthy population >0.5 for each

age/gender group) of the qHPV vaccine in cancer survivors. We are therefore extending the study to evaluate non-inferiority of the 9vHPV vaccine; interim data analysis results from the qHPV vaccine cohort indicate that an additional 200 patients will be sufficient to perform this evaluation in cancer survivors.

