8.2.2. Aim 2 (Vaccine Evaluation)

8.2.2.1. Determine immunogenicity of qHPV and 9vHPV vaccine 1 month following the third and final vaccine dose

The primary analytic approach will be per-protocol (PP)³⁰ analysis; intention to treat analysis will also be conducted. The evaluation will be completed separately for the qHPV and 9vHPV cohorts. The sample size is powered to determine whether vaccine-induced anti-HPV-16 and -18 neutralizing antibody response in cancer survivors is comparable to the age- and sex-matched general population (Table 7); PP immunogenicity population includes participants who are seronegative for the oncogenic vaccine components of primary interest (HPV-16, -18) on Day 1, complete all three vaccine doses within the protocol-specified time frames, and have immunogenicity data available at the time of analysis. Each vaccine component will be analyzed separately, and we will adjust for intensity of treatment. Anti-HPV-6 and -11 (and in the 9vHPV cohort, Anti-HPV-31, -33, -45, -52, and -58) response will also be explored. The primary outcome of interest is GMT. We will also assess seropositivity rates among cancer survivors. Seropositivity (binary variable) is defined as: qHPV cohort: Anti-HPV-6, -11, -16, and -18 titer ≥ 20 , 16, 20, and 24 mMU/ml respectively;³⁰ 9vHPV cohort: Anti-HPV-6, -11, -16, -18, -31, -33, -45, -52, and -58 titer ≥ 30 , 16, 20, 24, 10, 8, 8, 8, and 8 mMU/ml, respectively.⁶⁹

Outcome measure (GMT): Using the historical healthy population for qHPV²⁸ and 9vHPV⁶⁹ respectively, a multiplicity-adjusted 95% 2-sided confidence intervals for the ratio of mean GMT for HPV-16 and -18 in the cancer and healthy population will be computed. If the lower 95% limit is greater than 0.5, immunogenicity in cancer survivors will be considered non-inferior.³⁰

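### The eight HPV-16/-18 non-inferiority comparisons appear to rest on a flat 0.025/8 split that is valid but needlessly conservative; Holm's step-down holds the same error and shows at least as many, and more on average

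*Combined protocol and SAP*

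**What the plan says.** The sample-size text in 8.1 (Aim 2, qHPV cohort) says the planned numbers "will provide 80% power to demonstrate non-inferiority with respect to anti-HPV-16, and/or -18 GMT", "assuming a one-sided t-test, Type I error =0.00312 (for an overall Type I error =0.025"). Enrolment is tracked by four age-sex groups: "The coordinating center will track enrollment to each stratum (Younger Females, Older Females, Younger Males, Older Males"). The calculation assumes that "cancer survivors were similarly distributed in regard to immunogenicity with the same SD as in this healthy population", with a margin of half the healthy mean.

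The analysis text in 8.2.2.1 covers both cohorts, each evaluated on its own. It says "Each vaccine component will be analyzed separately" and calls for "a multiplicity-adjusted 95% 2-sided confidence intervals for the ratio of mean GMT for HPV-16 and -18". The decision rule is: "If the lower 95% limit is greater than 0.5, immunogenicity in cancer survivors will be considered non-inferior".

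The 9vHPV part of 8.1 describes the January 2016 interim look at the qHPV cohort (N=133). It expresses sufficiency through the "lower limit of the multiplicity-adjusted 95% confidence intervals for the ratio" exceeding 0.5 in each age-sex group, concludes that the 254 qHPV patients are ample, and sets the 9vHPV cohort at 200.

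No section names an adjustment method, mentions an ordered or step-down procedure, or gives a per-test level for the 9vHPV cohort.

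**The concern.** The only adjustment that the plan puts a number on is an equal eight-way split of 0.025. If the final analysis uses it, each comparison must clear 0.003125 however the others turn out. Suppose seven comparisons pass at 0.003 or below and the eighth has p=0.01. Under the flat split the eighth fails. Under Holm it is tested last, at 0.025, and passes with the same familywise error.

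The plan wants separate statements by HPV type and stratum. What is at stake is therefore how many of those eight statements the data can support, most of all in the 9vHPV cohort, which has the fewest patients per stratum.

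**Working it through.** **Inputs.** E, SD and N come from Table 7. Stratum sizes are the larger N per stratum: younger females 72, older females 77, younger males 82, older males 81 (total 312). The true ratio of 1 is the plan's assumption. Three inputs are not in the documents: the correlation between the two types within a stratum (0, 0.5 and 0.8 tried), equal strata with every patient evaluable for the smaller cohorts (254/4 = 63.5, taken as 63; 200/4 = 50), and the log-scale SD.

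**Step 1: reproduce the plan's figures.** 0.025/(2 × 4) = 0.003125, printed as 0.00312. For N, I used a one-sided one-sample t-test against a fixed historical mean, with noncentrality (E/SD)√n, level 0.00312 and power 0.80:

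| Stratum | HPV-16 computed / Table 7 | HPV-18 computed / Table 7 |
|---|---|---|
| Younger females | 70 / 72 | 68 / 69 |
| Older females | 79 / 77 | 61 / 58 |
| Younger males | 71 / 72 | 79 / 82 |
| Older males | 71 / 72 | 80 / 81 |

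The larger value per stratum gives 70 + 79 + 79 + 80 = 308 against 312. The small differences are expected, because the cited historical-control method also uses historical sample sizes that the documents do not give. At an unadjusted 0.025 the cells would need only 37 to 49. The plan was therefore sized for a flat split.

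**Step 2: the two procedures.** Bonferroni compares every p-value with 0.003125. Holm orders the p-values and compares the k-th smallest with 0.025/(9 − k), that is 0.003125, 0.00357, 0.00417, 0.005, 0.00625, 0.00833, 0.0125 and 0.025, stopping at the first failure. Each Holm level is at least 0.003125, so whatever Bonferroni rejects Holm also rejects. With all eight nulls true, the simulated familywise error is the same for both (0.022-0.024).

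**Step 3: Table 7's model.** True ratio 1, raw-titre SD, 200,000 simulated trials per scenario; ranges are over correlations 0 to 0.8.

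| Size | Mean shown of 8, Bonferroni | Mean shown of 8, Holm | All eight, Bonferroni | All eight, Holm |
|---|---|---|---|---|
| N=312, planned strata | 6.7 | 7.5-7.6 | 25-35% | 73-77% |
| 63 per stratum (assumed) | 5.8 | 6.9-7.0 | 8-15% | 48-56% |
| 50 per stratum (assumed) | 4.7 | 5.8 | 1-5% | 22-32% |

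At N=312, power per comparison rises from 79-91% to 93-98%, and Holm shows more comparisons than Bonferroni in 53-60% of trials. With a true ratio of 0.75 (correlation 0.5) the mean rises only from 1.6 to 1.8, and Holm shows more in 16% of trials.

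**Step 4: the log scale, natural for a GMT ratio.** With assumed SD 1.0 the noncentrality is ln(ratio/0.5)·√n. At 50 per stratum this is 0.693 × 7.07 = 4.90 for ratio 1 and 0.470 × 7.07 = 3.32 for ratio 0.8. Chance of showing all eight, correlation 0.5:

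| Per stratum | True ratio | Bonferroni | Holm |
|---|---|---|---|
| 63 | 1.0 | 97% | 99.8% |
| 63 | 0.9 | 76% | 97% |
| 63 | 0.8 | 24% | 70% |
| 50 | 1.0 | 83% | 98% |
| 50 | 0.8 | about 8% | about 44% |

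The size of the gain depends on the scale, the SD and the true ratio; its direction does not.

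**The case against.** Four points on the other side are fair.

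- **The method is not stated at analysis.** 0.00312 stands only in the sample-size text, and 8.2.2.1 leaves its adjustment unnamed. A reader might infer that the plan binds every final test to 0.00312; the documents do not say so. This stands, and it is a reason to name the method.
- **Bonferroni is valid.** It holds the stated 0.025, and its simultaneous intervals match a rule read from a lower limit. Holm has no equally simple intervals. This stands: the point is about efficiency.
- **The gain may be nil for qHPV.** One might conclude that non-inferior strata or types will be reported as not shown purely because of the procedure. The documents do not support that. Section 8.1 reports interim data indicating that 254 patients are enough for the adjusted limits to exceed 0.5 in every group, and if all eight clear those limits Holm adds nothing. The log-scale result at 63 per stratum and ratio 1 agrees. That interim rested on 133 qHPV patients, however, and does not settle the matter for 200 patients on another vaccine.
- **Timing.** qHPV immunogenicity data were examined in January 2016 against adjusted limits. Moving to a more permissive rule there afterwards is open to criticism.

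A further tempting reading is that the interim wording makes success an all-groups claim, for which no split is needed (each test at 0.025 gives 75-79% for all eight at N=312). That wording explains why the cohort is large enough; it does not define a single joint claim, and 8.2.2.1 analyses the components separately. The mean number shown is therefore the more relevant measure. Holm serves either reading.

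**Conclusion.** The point holds as an inexpensive improvement. The plan's one quantified adjustment is an equal eight-way split, and its analysis section names nothing else. Holm at the same one-sided familywise 0.025 needs no assumption about correlation and shows at least as many comparisons non-inferior.

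On the plan's own model the average gain is about 0.8 to 0.9 of a comparison at N=312 and about 1.1 at 50 per stratum. The gain is negligible if survivors respond like the healthy population on the log scale with 63 per stratum. It is substantial at 50 per stratum if the true ratio is nearer 0.8, and small again by 0.75 on the raw scale. Figures for 63 and 50 per stratum rest on assumed equal strata and full evaluability; log-scale figures also rest on SD 1.0 and correlation 0.5. The 9vHPV cohort has the most to gain and is the only one for which the change is cleanly prospective.

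**What to change.** In 8.2.2.1:

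1. State that, for the 9vHPV cohort, the eight hypotheses (GMT ratio at or below 0.5; HPV-16 and -18 in four strata) are tested by Holm's step-down at one-sided familywise 0.025. Adopt this before that cohort's analysis.
2. For the qHPV cohort, keep the existing rule and name its method. If Holm is applied there, disclose that interim immunogenicity data had been seen.
3. Where Holm applies, reword the decision rule so that non-inferiority is concluded from Holm-adjusted p-values.
4. Report the Bonferroni simultaneous intervals descriptively, two-sided 99.375% each (1 − 2 × 0.003125). Unadjusted 95% intervals beside Holm p-values could show a lower limit above 0.5 for a comparison that fails; these intervals cannot.
5. Keep 0.00312 in 8.1 as a conservative planning level.

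The change needs no additional patients. It does replace the decision rule: the conclusion is no longer read from one simultaneous interval, and a comparison may pass under Holm while its 99.375% lower limit lies below 0.5. The text should say that this can happen.

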9.2 Monitoring and Personnel Responsible for Monitoring

The UAB DSMC (UAB CTMC-Clinical Trials Monitoring Committee) will serve as the safety board of record for this study.

The Protocol Management Team (PMT), consisting of the co-PIs, co-investigators, CRA, protocol nurse, and statistician, is responsible for monitoring the data and safety of this study, including implementation of any stopping rules for safety and efficacy.

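### The qHPV analysis makes no allowance for the January 2016 interim look that informed the smaller cohort, so the stated overall 0.025 is not guaranteed

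*Combined protocol and SAP*

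**What the plan says.** Section 8.1 sizes the qHPV cohort per protocol: "Sample size required = 312", the sum of the four stratum targets in Table 7. The test is one-sided against historical means, with "Type I error =0.00312 (for an overall Type I error =0.025". The same paragraph says that each stratum closes when its target of evaluable participants is reached.

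The 9vHPV paragraph of 8.1 then reports the look: "Results of interim data analysis on the qHPV vaccine cohort (performed in January 2016", with 133 participants who had a Month 7 sample. It concludes that the 254 enrolled by 3-1-16 will be ample to address non-inferiority. It defines non-inferiority as a lower limit above 0.5 for HPV-16 and -18 in every age/sex group, and gives this conclusion as the reason for extending the study to 9vHPV.

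Section 8.2.2.1 asks for a multiplicity-adjusted interval and a lower limit above 0.5. It gives no per-comparison level and does not mention the look. Section 9.2 makes the management team responsible for monitoring, "including implementation of any stopping rules for safety and efficacy". Section 9.4 contains a toxicity rule only. No interim level, boundary or spending function appears anywhere.

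**The concern.** A level of 0.00312 holds its nominal error when the sample size is fixed or is changed for reasons unrelated to the results. Here the primary comparison was examined part-way, and what was seen helped to decide that a smaller cohort would do. Stopping short after a good interim estimate preserves a favourable chance fluctuation that further accrual would tend to dilute. Because the eight comparisons already use all of the 0.025, there is no reserve to absorb this.

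At stake is whether a reader can rely on the stated error rate and interval coverage for the qHPV primary endpoint. The plan offers this endpoint as evidence for vaccination recommendations in survivors.

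**Working it through.** **Inputs from the documents.** One-sided 0.00312 per comparison, overall 0.025, 312 per-protocol, attrition 96% then 92%, and Table 7 margins and SDs (8.1, qHPV paragraph); 133 at the look and 254 enrolled (8.1, 9vHPV paragraph).

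**Assumptions.** Normal test statistics; information proportional to N and the same fraction in each stratum; historical means treated as fixed; all 133 count towards the final analysis.

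**1. The plan's own figures.**
- Level: 0.025/8 = 0.003125, and 8 × 0.00312 = 0.02496. The critical value is z = 2.73.
- Sample size: a one-sample t calculation with Table 7's margins and SDs at 80% power, taking the larger N in each stratum, gives 70 + 79 + 79 + 80 = 308. The plan has 72 + 77 + 82 + 81 = 312. The figure is reproduced closely.

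**2. Size of the cut.**
- Plan: 353 × 0.96 = 339, and 339 × 0.92 = 312.
- After the look: 254 × 0.96 × 0.92 = 224.
- So 353 to 254 enrolled, or 312 to about 224 per-protocol.

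**3. The look only shortened accrual, with one final test.** Let Z1 be the statistic at 133. The final N is n (254 or 224) if Z1 > k, otherwise 312. Given Z1 = x, the chance of a false claim at final size N is 1 − Φ[(2.73√N − x√133)/√(N − 133)]. Integrating over x and maximising over k:

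| Final N | Worst k | Error per comparison | Bound over eight | If eight independent |
|---|---|---|---|---|
| 254 | 1.9 | 0.0035 | 8 × 0.00349 = 0.028 | 0.0276 |
| 224 | 1.95 | 0.0038 | 8 × 0.00375 = 0.030 | 0.0296 |

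Correlation between HPV-16 and -18 lowers the overall figure. With one look it falls from 0.0247 (independent) to 0.0188 at an assumed correlation of 0.9, a ratio of 0.76. Scaling by that ratio gives approximately 0.0276 × 0.76 = 0.021 and 0.0296 × 0.76 = 0.022, both under 0.025. At a correlation of 0.5 the ratio is 0.0237/0.0247 = 0.96, giving about 0.026 and 0.028.

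**4. A claim possible at either look, each at 0.00312.** The two statistics are bivariate normal with correlation √(133/254) or √(133/224).
- Error per comparison: 0.0055 or 0.0054.
- Bound over eight: 0.044 or 0.043.
- At 133/254 with HPV-16/-18 correlation from 0.5 to 0.9, the overall figure is 0.042 to 0.033.

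**5. Success requires all eight.** A false joint claim needs a false claim on at least one particular comparison. Its probability is therefore at most the per-comparison error: 0.0038 under step 3, about 0.0055 under step 4.

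**6. What a valid method costs.**
- Fixed-weight combination: Z = √(133/312)·Z1 + √(179/312)·Z2, compared with 2.73, where Z2 uses later participants only. Precision is proportional to √(133/312)·√133 + √(179/312)·√(N − 133). At N = 254 this is 15.86 against √254 = 15.94, so intervals are 0.5% wider. At N = 224 it is 14.76 against 14.97, so 1.4% wider.
- Equal two-look boundaries holding 0.003125: z = 2.92 (254) or 2.91 (224), a one-sided level of about 0.0017-0.0018. Interval width rises by 2.92/2.73 = 1.07.

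**The case against.** The strongest case is that no excess error has been shown.

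- **The look may have been only a projection.** The wording about sufficiency is in the future tense and vaccination was still under way. No result is declared, and the clause about a limit above 0.5 defines non-inferiority rather than reporting an interim test. This stands. A reader might infer that non-inferiority was claimed, or could have been, in January 2016. The documents do not say so, and the 0.044 depends on it.
- **The change of vaccine had an outside cause.** The abstract says that 9vHPV was licensed, recommended and rapidly replacing qHPV in practice, and the cohort ended on a calendar date. If the cut owed nothing to the results, there is no inflation. This stands in part, but 8.1 itself rests the decision on the interim results. Under the plan's original inputs, 224 per-protocol participants give only about 59-63% power per stratum, so the statement that the cohort is ample must draw on what the interim data showed.
- **The success rule may be all-eight.** The 9vHPV paragraph refers to every age/sex group, and under that rule the joint error is far below 0.025. Yet the sample-size paragraph says the design "will provide 80% power to demonstrate non-inferiority with respect to anti-HPV-16, and/or -18 GMT in cancer survivors", and 8.2.2.1 analyses each component separately. The rule is unsettled.
- **The final level is not stated.** A reader might infer that the final test uses 0.00312 unchanged. That figure appears only in the sample-size text. It is the only adjustment quantified, but 8.2.2.1 does not repeat it.
- **Section 9.2 is generic.** Its reference to any efficacy rules does not show that one existed and was left out.

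**Conclusion.** The point holds as a failure to guarantee the stated error control. The plan spends the full 0.025 on eight comparisons at a fixed size, reports a look at the primary comparison that informed a smaller cohort, and makes no allowance for it.

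The documents do not support saying that 0.025 is exceeded. Accrual-only inflation is modest: an overall bound of 0.028-0.030, reached only if the cut followed the least favourable threshold rule for every comparison at once, although one decision covered the whole cohort. Strong correlation between the two types could bring it below 0.025. The larger figure needs a possible claim at the look. An all-eight rule protects the joint conclusion, but the stratum and type claims and their simultaneous intervals would still lack their stated level.

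Nor is the reduction one from 312 to 254, as a quick reading suggests, since the first figure is per-protocol and the second is enrolled. The 224 assumes that the plan's attrition rates held.

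The 9vHPV cohort is analysed separately, so this error calculation does not apply to it.

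**What to change.** In 8.1 and 8.2.2.1, record the January 2016 look: whether it was planned, what was computed, whether a claim was possible and at what level, and how it led to the cohort decision. State the final per-comparison level and whether success means any or all of the eight comparisons.

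Then run the final qHPV tests and intervals with a method that is valid after the look:

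- **If no claim was possible at the look:** use a fixed-weight combination of the first 133 and the later participants, with weights from the planned sample (133 and 179 of 312). Within each stratum, use its interim count and the remainder of its Table 7 target.
- **If a claim was possible:** use a two-look level instead, about 0.0017 one-sided with equal boundaries. This level is not compulsory. O'Brien-Fleming-type spending would leave about 0.0031 for the end, but only with about 0.00004 (133/254) to 0.0001 (133/224) at the interim. Any other boundary is acceptable only if it matches the level actually used at the interim.

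The cost is SAP text, some extra analysis work, and qHPV intervals up to about 7% wider on the log scale (about 0.5-1.4% with the combination method). No extra patients are needed.
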